**‘WOULD YOU LIKE TO BE IN THE STUDY?’ ”**

Referral information for alcohol/substance/sedative use and legal counseling in use at WRNMMC will be maintained in the clinical area where screenings are conducted. These are commonly posted and displayed for any individual to review. In general, these materials are also maintained with other health and welfare referrals so anonymity and privacy is maintained. As the participant leaves, the research clinician will inform the participant that resources are available should they be interested. If the research clinician feels the individual is at personal risk, active intervention will be necessary as detailed in Section 6.3. a.

Exclusion of acute or unstable medical illnesses: This would prevent subjects from tolerating the acute trial target doses of medication. We will include subjects with chronic stable medical illnesses.

Exclusion of women who are pregnant, plan to become pregnant or are breast-feeding : The study medication is a Category C drug, and we cannot be certain that it will not have teratogenic effects and it may be present in breast milk. As such, the Consent Form advises female participants to avoid becoming pregnant for at least one month after last receiving the study drug. Pregnancy within this time after the study drug is given may be a risk to an unborn baby. No evidence of teratogenic effects is found in the literature for males; however, all participants will be advised of the pregnancy category of the drug (C) and be informed that they should avoid attempting to conceive during participation or for at least one month after last receiving the study drug. Female participants will be given a pregnancy test post-treatment.

Because it is unknown whether riluzole can adversely affect human sperm, male participants will be informed of the possible risk to a child conceived while using the study drug and be advised they avoid engaging in sexual activity with the intent to conceive.

## Recruitment and Consent

### 13.1 Identification and Selection of Subjects:

See Legacy Protocol

### 13.2 Recruitment Process:

Subjects will be recruited from collaborator- and provider-referrals at WRNMMC and the Syracuse VA Medical Center, as well as from associated community-based outpatient clinics (CBOCs) and other referring research studies drawing from current patients with PTSD, with or without mild TBI, who are sub-optimally responsive to their current medication treatment over a minimum of 8 weeks. We intend to use office space in the WRNMMC Behavioral Health Clinic. Collaborators and providers will identify these potentially eligible patients and discuss with them the possibility of participating in the study.

During the standard of care intake or initial evaluation process, collaborators and providers will give referral patients the contact information to reach the study research staff only if they express interest in contacting the study research staff and learning more information about participating in the study, specifically, the inclusion and exclusion criteria necessary for study participation. Referral interactions with study research staff may occur by telephone, email, text and/or instant messaging, as well as in person at WRNMMC. Patients who then meet inclusion criteria will be scheduled for the Screening Visit once informed consent is obtained. All advertisements and information to be given to potential participants regarding how to contact study staff if interested will be approved by the IRB prior to dissemination. Advertisements will include posters, trifold brochures, and provider handouts, which will be disseminated at Walter Reed National Military Medical Center services and intranet, and posting on clinicaltrials.gov and Facebook. To ensure confidentiality, on the study Facebook page, only study personnel will be permitted to post information; potential participants and providers may privately message and "Like" or "Share" the page. All PI information for participants and enrollees will be maintained in secured files or electronic storage under locked quarters. Only Research Staff will have access to these records. This is further detailed in Section 6.3.c.

All subjects will be evaluated for study entry during the Screening Visit by a Masters-level Clinical Research Psychologist under the supervision of a credentialed provider within the WRNMMV Behavioral Health Clinic using a CAPS assessment; WRNMMC study research staff will recruit, screen, consent and enroll subjects at WRNMMC, while Syracuse VA Medical Center study research staff will recruit, screen, consent and enroll subjects at the Syracuse VA Medical Center, as well as from associated community-based outpatient clinics (CBOCs). CAPS score  $\geq$  40 will be necessary for study enrollment. Those entering the study at the completion of an INTRuST medication trial will also receive a CGI assessment, and must have an assessment determination of "NOT improved" or "NOT very much improved" on the CGI at the completion of their medication trial to be eligible for study enrollment.

The Screening Visit will include all screening tests, patient and family history, and psychiatric and physical examinations, as well as menstrual history in females. Inclusion and exclusion criteria will be assessed. Subjects will undergo a physical exam, supine and standing vital signs, blood chemistries, liver function tests, hematology profile, urinalysis (including screens for substances of abuse), hepatitis screen, SCID, and CAPS. Women of childbearing capacity will have baseline serum  $\beta$ -HCG, and a positive  $\beta$ -HCG will exclude them from participating in the study. Subjects must also have a negative Human Immunodeficiency Virus (HIV) test.

A complete medication list will be compiled prior to dispensing riluzole and verification of the list for change will be done at the weekly clinical visit to assess for compounds that may interact with clearance of the drug.

Participants will be advised to take riluzole 1 hour before or two hours after meals for optimal metabolism of the compound. Education will be provided that the bioavailability of the compound is significantly affected by high fat meals and that charbroiled food may increase the speed of clearance of the compound from their bodies.

### 13.3 Compensation for Participation:

Compensation is provided for off-duty military personnel participating at WRNMMC and for participants recruited from the Syracuse VA and associated CBOCs. Reimbursement is determined by the number of hours spent completing study assessments and equates generally to a rate of \$15 per hour. Reimbursement will be pro-rated for incomplete research sessions. Reimbursement is not

provided for treatment visits. Reimbursement will be issued as a gift card given directly to the participant (WRNMMC) or as a check mailed to the participant's home (Central New York Research Corporation (Syracuse VA and associated CBOCs).

Participant Reimbursement

Visit	Rate	Hours	Reimbursement
Screening	\$15	5	\$ 75
Visit 1	\$15	4	\$ 60
Visit 2	\$15	2	\$ 30
Visit 3	\$15	2	\$ 30
Visit 4	\$15	2	\$ 30
Visit 5	\$15	4	\$ 60
Visit 6	\$15	2	\$ 30
Visit 7	\$15	2	\$ 30
Visit 8	\$15	2	\$ 30
Visit 9	\$15	4	\$ 60
Bonus for attending all clinical sessions			\$ 80
Bonus for completing both  H MRS imaging scans (pre and post)		5	\$ 75
Total Reimbursement per participant			\$ 590

**13.4 Eligibility Assessment Process:**

See Legacy Protocol

**13.5 Consent Process:**

Are you requesting a waiver or alteration of informed consent?

Yes  No

Please explain the consent process:

- A. Informed consent will be collected at the start of screening. Participants will only be assigned a study ID number upon randomization after successfully being screened in. Any participant who is found to be ineligible after screening will not be randomized or assigned a study ID number, however their consent and screening data will be stored with the rest of the study data files. The stated recruitment goal of 158 participants approximately refers to consented participants and does include participants who were not randomized because of screen failure or any other ineligibility factor.

Informed consent and HIPAA authorization will be administered by a member of the research team at each site prior to screening and psychological testing and is a process that is initiated prior to the individual's agreeing to participate in the study and continuing throughout the individual's study participation. risks and possible benefits of the study and opportunity to fully review the consent form, and ask questions. The individual will be given sufficient opportunity to discuss the study and process the information in the consent process prior to agreeing to participate. As a part of this process, all subjects are informed that they are not obligated to participate in this study, and the rights and welfare of the participants will be protected by emphasizing to them that the quality of their medical care as well as the care to which they are entitled to in their referring research study participation will not be adversely affected or penalized if they decline to participate in this study. If they choose to take part in the study, they will be asked to sign the consent form. This process will be monitored as required at each participating institution and in accordance with all regulatory guidelines. Patients will be informed of their right to withdraw from the study at any time prior to obtaining informed consent and at subsequent scheduled visits. This is anticipated to be a time commitment of one hour.

- B. After the subject has been given ample time to read the consent document, the consentor will ask him or her to briefly explain the document. At this time, any questions will be answered. If in the judgment of the consentor the subject does not understand, the subject will be excluded; the consentor will then try to explain the reason for exclusion as best as possible.

C. The subject will verbally list health information to be accessed and released to ensure complete understanding. If, in the judgment of the consentor, the subject is not able to understand the health information to be accessed and possibly released, the subject will be excluded; the consentor will then try to explain the reason for exclusion as best as possible.

D. A HIPPA waiver will not be requested.

**13.6 DoDI 3216.02 requires an ombudsman to be present during recruitment briefings when research involves greater than minimal risk and recruitment of Service members occurs in a group setting. If applicable, you may nominate an individual to serve as the ombudsman.**

- N/A
- Propose ombudsman

**13.7 Withdrawal from Study Participation:**

Explain the process for withdrawal and specify whether or not the subjects will be given the opportunity to withdraw their data their data/specimens in the event they wish to withdraw from the study

See Legacy Protocol

## 14.0 Risks and Benefits

### 14.1 Risks of Harm:

Identify all research-related risks of harm to which the subject will be exposed for each research procedure or intervention as a result of participation in this study. Consider the risks of breach of confidentiality, psychological, legal, social, and economic risks as well as physical risks. Do not describe risks from standard care procedures; only describe risks from procedures done for research purposes

**General:** By agreeing to participate in this study, subjects will be temporarily forgoing the opportunity to receive routine clinical care and psychiatric medication in the community. This will be clearly explained to all patients, along with the treatment strategies that are generally used in patients with PTSD. Patients will also be told that riluzole is available for prescription by physicians in the community. However, it has not received FDA approval for the indication of PTSD.

**Screening and Evaluation:** The risks and discomforts of the screening and baseline evaluations are minimal. No discomfort is expected to be associated with the physical examination or the clinical interview. Venipuncture may be associated with the momentary discomfort of the needle stick, as well as a small risk of hematoma (bruise) formation. Subjects will be exposed to the discomfort of asking personal questions that they may find distressing.

**Stabilization Period and Treatment Trial:** Since it is unknown whether riluzole is effective in the treatment of PTSD, participation in this trial could delay additional potentially effective treatments by 10 weeks. That is, participation in this study would preclude a subject from receiving other potential augmenting medications (although none are FDA approved for PTSD) or additional psychotherapy for his or her refractory PTSD. If the patient is discontinued from the study due to a worsening of their illness, they will receive standard care.

**Risks Due to Riluzole Administration:** Controlled studies in medically ill patients taking multiple concomitant medications indicate that it is well tolerated. The most frequent dose-related adverse events included nausea, asthenia, and elevated liver enzyme levels. Less frequent dose-related adverse events include exfoliative dermatitis and tremor. Nausea was reported by 12 to 21% of riluzole-treated patients, compared with 12% for placebo. Less than 1% of patients with asthenia discontinued treatment. Dizziness, diarrhea, anorexia, and circumoral paresthesia occurred more frequently with 200-mg/day riluzole. It should be noted that concomitant medications were permitted in the trials that examined riluzole, thus adverse events may be over-reported (approximately 72% took at least one

concomitant medication, the mean number of concomitant medications per patient during this trial period of 6.6). Elevated ALT levels (>5 X ULN) accounted for the majority of treatment discontinuations based on laboratory adverse events. This event represented less than 4% with any treatment group (50 mg, 100 mg, or 200 mg riluzole) (Lacomblez et al 1996).

Another potential side effect of riluzole that has been reported to rarely occur is neutropenia. In ALS trials, three out of 4,000 patients given riluzole developed marked neutropenia, all seen within the first 2 months of riluzole treatment. Because of the risk of an elevation of liver enzymes and neutropenia, we will exclude patients with a history of significant liver disease or neutropenia. Of note, is that in one of these trials, approximately 72% took at least one concomitant medication, the mean number of concomitant medications per patient during this trial period of 6.6. It is possible that other medications, concomitant medical illnesses, etc could account for these cases of neutropenia. In our preliminary studies, approximately 33 subjects with major depression were exposed to riluzole. Overall the drug was well tolerated and no serious adverse events occurred. Another potentially serious but very rare event is pancreatitis.

Our (NIH) experience with riluzole is outlined below:

An 8-week open-label study with riluzole in treatment-resistant DSM-IV bipolar depression (Protocol #03-M-00092) (Zarate et al., 2005). Eight subjects (57%) completed the 8-week trial. The reasons for discontinuation were adverse events (N =3; 2 asymptomatic increase in liver function tests, 1 renal calculi) and lack of improvement (N =3). Patients received riluzole at a mean daily dose of 171.4 + 42.6 mg (79% took a dose of 150 mg/day or more). The most common adverse events during the trial were fatigue (N = 4), decreased salivation (N = 4), reduced sleep (N = 4), nausea (N = 3), diarrhea (N = 3), weight loss (N = 3), decreased sex drive (N = 3), blurred vision (N = 3), and headache (N = 3). No serious adverse events were noted. Two subjects were discontinued from the study because of increased liver function tests (LFTs) that were more than three times the upper normal limit. These subjects were asymptomatic for hepatic dysfunction, and LFTs normalized shortly after discontinuing riluzole. One additional subject was discontinued because of renal calculi. Overall riluzole was well tolerated.

A 6-week open-label study with riluzole in treatment-resistant DSM-IV major (unipolar) depression (Protocol #02-M-0034) (Zarate et al., 2004). Patients received riluzole at a mean daily dose of 168.8 + 27.2 mg (84.2% took a dose of 150 mg/day or more) for a mean duration of 5.4 ± 3.7 weeks. Sixty-eight percent (N=13) of subjects completed the 6-week trial. The reasons for discontinuation were adverse events N=3 (1 increased liver function tests, 1 malaise, 1 nausea/vomiting), non-response N=2, and administrative N=1. The most common adverse events during the trial were headache (58%), gastrointestinal distress (nausea or vomiting) (43%), decreased salivation (47%), constipation (32%), and tension/inner unrest (26%); similar side effects have been observed with riluzole in ALS trials (Bensimon et al., 1994). No serious adverse events were noted. One subject was discontinued from the study because of an increase in liver function tests (LFTs) that was 3 times the upper normal limit. This subject was asymptomatic for hepatic dysfunction, and LFTs normalized shortly after discontinuing riluzole. There was no relationship between dose of riluzole and adverse events or changes in laboratory tests.

A condition called interstitial lung disease has occurred in some patients who have taken riluzole. Participants will be advised of this risk and informed that should they develop a dry cough with shortness of breath or difficulty breathing, they will need to seek medical attention including a chest x-ray assessment and will need to discontinue taking riluzole immediately.

**Risks Associated with Magnetic Resonance Spectroscopy:** H MRS is not associated with any known deleterious biological effects in normal subjects. However, there are risks for subjects who have any metallic implants in their body or who have an artificial cardiac pacemaker. For this reason, they will be screened for the presence of any metallic prostheses or cardiac pacemaker both at the time of recruitment, and just prior to H MRS imaging. Subjects will be advised of two potential discomforts. The first is that the procedure requires remaining still while lying on their back for an extended period of time (up to 60 minutes). The second is the MRS machine is a tightly enclosed space, which may be of concern for those with claustrophobia.

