Subjects will also complete the screening visit where they will be evaluated for study entry and enrollment. Psychiatric history and diagnosis will be administered by study staff at each site using the SCID-P (First et al., 1995) and the DSM-IV Diagnostic Criteria (American Psychiatric Association, 1994). Patients who meet DSM-IV criteria for PTSD must have a Clinician Administered PTSD Scale (CAPS) of 40 at Visits 1 and 2 to be included in the study. Those entering the study at the completion of a referring INTRuST or other medication trial for PTSD will also receive a CGI assessment, and must have a score indicating "NOT improved" or "NOT very much improved" on the CGI scale at the completion of their medication trial to be eligible. The screening visit will include the screening tests, patient history, and psychiatric and physical examinations, as well as menstrual history in females. Subjects will undergo a physical exam, supine and standing vital signs, complete blood cell counts (CBC) with differential, electrolytes, thyroid function test, liver function tests, fasting blood sugar, hematology profile, urinalysis (including screens for substances of abuse), hepatitis screen, SCID, and CAPS. Women of childbearing capacity will have a baseline serum  $\beta$ -HCG. A positive  $\beta$ -HCG will exclude them from participating in the study. Subjects must also have a negative Human Immunodeficiency Virus (HIV) test. Results of these tests will identify patients who should be excluded because of active medical problems or substance abuse that might affect the clinical phenomenology or treatment response and to identify conditions that might make randomization into one of the treatment arms less safe. The CGI will be used to collect information on overall improvement, and the UKU side effect rating scale will be used to collect information on side effects. Finally, eligible subjects who consent to participate in the baseline  $^1\text{H}$  MRS portion of the study will undergo the scan during the screening visit.

The time commitment for the telephone confirmation is estimated to be 10 minutes. The screening visit will take 4 hours. The time commitment for the baseline  $^1\text{H}$  MRS scan is estimated to be 60-90 minutes.

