## 12.6 Exclusion Criteria:

Order Number	Criteria
	
b. Exclusion Criteria - Subjects will be excluded from the study for any of the following reasons:
 
 
1. Female subjects of childbearing capacity who test positively for <math>\beta</math>-HCG, or are either self-reporting as pregnant, planning to become pregnant, or nursing.
 
2. Presence of psychotic features.
 
3. Unable to provide informed consent or comply with study procedures.
 
4. Previous treatment with riluzole.
 
5. Serious, unstable illnesses including hepatic, renal, gastroenterological, respiratory, cardiovascular (including ischemic heart disease), endocrinologic, neurologic, immunologic, hematologic disease, or HIV. This includes individuals with a history of COPD by diagnosis as well as persons taking inhalers for Asthma or Reactive Airway Disease.
 
6. Clinically significant abnormal levels (3x ULN or greater) of serum transaminases (ALT/SGPT; AST/SGOT), current or past blood dyscrasia.
 
7. Subjects with uncorrected hypothyroidism or hyperthyroidism.
 
8. DSM-IV alcohol or substance abuse or dependence within 90 days of the screening visit.
 
9. Treatment with a reversible MAOI, guanethidine, or guanadrel within 1 week, or any change in fluoxetine dosing within 8 weeks prior to visit 2. Use of antidepressant and sedative/hypnotic drugs at stable dose is permitted.
 
10. Documented history of hypersensitivity or intolerance to riluzole.
 
11. Subjects with a current or past history of other axis I disorders including schizophrenia, schizoaffective disorder, bipolar disorder or dementia. However, those with a co-morbid history of other Axis I disorder like major depression, dysthymia or other anxiety disorders will be included; the justification for this is that approximately 70% of subjects with PTSD have co-morbid depression and or alcohol abuse, and restricting the sample to PTSD patients without depression will not accurately reflect the scope of this disorder.
 
12. Patients who are currently at high risk for homicide or suicide, as indicated by an affirmative answer to the question: "In the last three months, have you attempted to kill yourself, made specific plans to kill yourself, or had the intention to kill yourself?"
 
13. Current or planned litigation regarding the traumatic event.
 
14. Patients who recently started trauma focused cognitive behavioral psychotherapy (Patient's underlying educational or supportive individual or group therapy will be included).
 
15. Patient's actively enrolled in an evidence based psychotherapy treatment (e.g., Cognitive Processing Therapy or Prolonged Exposure Therapy) will be excluded until that therapy has concluded, but may be re-approached at that time if patient self-report or clinician referral suggests persistent PTSD symptoms upon conclusion of that treatment.
 
16. Subjects with an artificial cardiac pacemaker or metallic implants within their body will be enrolled at WRNMMC for the placebo-control clinical trial portion of the study only. These individuals, due to their pre-existing medical condition, are medically ineligible to participate in the <math>^1\text{H}</math> MRS imaging portion of the study. Further, the Magnetic Resonance (MRI) Screening Form is use at WRNMMC will be used for participant screening prior to any imaging procedures.
 
17. Use of benzodiazepines.
 

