Continuous monitoring of the participant's health while taking the assigned medication is performed by the Medical Monitor in conjunction with the Principal and Associate Investigators during the scheduled weekly visits. Participants will have clinical biochemistry laboratory blood assays performed to monitor their liver state and function. Liver Function Test (LFTs) will be run first at the Screening Visit and then weekly while taking the assigned medication. In the period between screening and randomization, the participant will be instructed not to begin taking study medication until the Investigator confirms that LFTs are within normal limits. Specifically, their alanine transaminase (ALT), aspartate transaminase (AST), total/direct bilirubin, and alkaline phosphate, will be monitored on a weekly basis during Study Period II to ensure that participants do not have liver function tests elevated over 3x normal ranges. If elevated LFTs are encountered, the test will be repeated, and if levels remain elevated at or above 3x upper limit of normal, the participants on the higher dose will have their dose reduced to 100mg per

day and participants on the low dose will be removed from the study. If a participant's LFTs ever exceed 5x upper limit of normal, the study drug will be discontinued and the subject will be withdrawn from the study.

Elevated LFTs of only 2xs level are not clinically uncommon and are often associated with any number of unrelated medical conditions or complications. A mild elevation in LFTs is quite often temporary in nature, and quickly reversible. Initial studies in riluzole established the 3x level as diagnostic for liver enzyme impairment or disruption to ensure that unrelated medical conditions and complications do not compromise the study while still ensuring the highest safeguarding of the participant.

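### Section 14.1 excludes a history of significant liver disease, but the 12.6 exclusion list does not carry that rule and its rationale admits chronic stable illness

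*Combined protocol and SAP*

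**What the plan says.** Section 14.1 (Risks Due to Riluzole Administration) gives a rule and its reason. Because riluzole can raise liver enzymes and cause neutropenia, "we will exclude patients with a history of significant liver disease or neutropenia". The rule depends on history. It does not require the disease to be unstable now or the LFTs to be abnormal now.

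In 12.6, two items bear on the liver:

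- Item 5 bars "Serious, unstable illnesses including hepatic, renal, gastroenterological, respiratory, cardiovascular" and other disease. It then names two respiratory groups as included: people with a past COPD diagnosis, and inhaler users with asthma or reactive airway disease. It names no liver history.
- Item 6 bars "Clinically significant abnormal levels (3x ULN or greater) of serum transaminases" and also "current or past blood dyscrasia".

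The rationale after 12.6, in its paragraph on acute or unstable medical illness, says: "We will include subjects with chronic stable medical illnesses". It makes no exception for the liver.

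Two other places are relevant. The Phase I screening text says of the laboratory and other tests: "Results of these tests will identify patients who should be excluded because of active medical problems". It adds that they should also pick up conditions that would make randomization less safe. Section 14.2(a) says that between screening and randomization "the participant will be instructed not to begin taking study medication until the Investigator confirms that LFTs are within normal limits".

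**The concern.** Section 14.1 tells the IRB how a known drug risk is controlled: patients with a significant liver history are kept off riluzole. Site staff normally check eligibility against the list in 12.6, not against the risk section. If the list omits the rule, staff following it correctly can randomize a patient whom 14.1 says is excluded on safety grounds.

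The omission does not look like a general drafting style. Section 12.6 writes in history where it wants it: COPD in item 5 and blood dyscrasia in item 6. The second of these matches the neutropenia half of the 14.1 sentence. Only the liver half has no counterpart.

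What is at stake is patient safety and consistent eligibility decisions across the two sites. The efficacy result is not at stake.

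**Working it through.** **The wording check.** Take a patient with past or chronic stable significant liver disease and normal LFTs, and apply each text in turn.

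| Text | Condition | Result for this patient |
|---|---|---|
| 14.1 | Significant liver disease in the history | Excluded |
| 12.6 item 5 | Serious and unstable hepatic illness | Not excluded (not unstable) |
| 12.6 item 6 | Transaminases at 3x ULN or more | Not excluded (normal) |
| Rationale after 12.6 | Chronic stable illness admitted | Chronic stable case included; past case not addressed |
| 14.2(a) pre-dose check | LFTs within normal limits | Passed |
| Phase I screening text | Active problems, or conditions making randomization less safe | Left to judgment; no liver-history rule |

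For the chronic stable case, 14.1 and the rationale give opposite answers. For the past case, only 14.1 excludes.

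**The risk behind the rule.** Section 14.1 summarizes two earlier open-label riluzole studies. Their sizes follow from the completion figures:

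- Bipolar depression: 8 completers are given as 57%. 8/14 = 57.1%, so n = 14. In this study, "Two subjects were discontinued from the study because of increased liver function tests (LFTs) that were more than three times the upper normal limit": 2/14 = 14.3%.
- Unipolar depression: 13 completers are given as 68%. 13/19 = 68.4%, so n = 19. One patient stopped for an LFT rise to 3x the upper limit: 1/19 = 5.3%.
- Together: 14 + 19 = 33, which agrees with the approximately 33 exposed subjects that 14.1 reports. (2 + 1)/33 = 9.1%, Clopper-Pearson 95% CI 1.9% to 24.3%.

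These rates are not broken down by liver history. They show why the rule exists and do not estimate the extra risk in the uncovered group.

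**Effect of the fix on sample size.** Inputs from 11.2: difference 9, SD 15, two-sided alpha 0.05, two-sample t test, up to 158 consented, 30-40% ineligible.

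Power comes from the noncentral t distribution with noncentrality (9/15)/√(1/n₁ + 1/n₂) and n₁ + n₂ − 2 degrees of freedom.

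- The plan's own case, 50 + 50: power 0.844, as stated in 11.2.
- Left after ineligibility: 158 × 0.70 = 110.6 and 158 × 0.60 = 94.8, so about 111 to 95.
- Worse case, 95 in total: power 0.825.
- With 1 further screen failure (94): 0.821. With 5 (90): 0.804.

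The range of 1 to 5 further failures is an assumption. All these figures are before dropout.

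**The case against.** The strongest reply is that this is an omission and not a contradiction. The 12.6 list does not claim to be complete, 14.1 is itself a binding statement, and both can be obeyed by applying every exclusion wherever it appears. On that reading the specific liver rule simply qualifies the general sentence about stable illness. This is a sensible way to resolve the conflict, but the protocol does not say so, and someone working from 12.6 and its rationale would not know that a resolution was needed.

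A second reply is that item 5 is broader than it looks, since it treats a past COPD diagnosis as falling under serious, unstable illness. That cuts the other way at least as strongly: history was written in for COPD and not for the liver. It is true that neither *serious* nor *significant* is defined, so how far the two terms differ is partly interpretation.

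A third reply is that screening narrows the gap. Patients have a medical history, a physical examination and a hepatitis screen, and LFTs must be normal before dosing, which is stricter than item 6. This stands, and it is why the point is minor. None of these steps states what to do with a liver history, and the patient in question passes the LFT check.

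Two limits also stand. Sections 13.1 and 13.4 refer to a Legacy Protocol that is not among the documents, and a liver-history check could be there. And the 9.1% should be read beside the ALS dose-ranging result in 14.1, where ALT above 5x ULN occurred in less than 4% of any treatment group. That is a different threshold and population, but a lower figure.

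**Conclusion.** The concern holds as a minor internal contradiction. Section 14.1 excludes patients with a significant liver history. Section 12.6 and its rationale, read as written, do not, and for a chronic stable case they say the reverse. The number of patients affected is unknown, because the documents give no rate of past or chronic liver disease in this population.

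The likely harm is limited by the screening review, the normal-LFT requirement before dosing, weekly LFTs, and the dose-reduction and stopping rules at 3x and 5x ULN. All three earlier LFT discontinuations were asymptomatic and resolved. The primary efficacy analysis is not affected.

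The conclusion rests on the text of 14.1, 12.6 and the rationale after 12.6. It makes no claim about what the Legacy Protocol contains or what sites do in practice.

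**What to change.** Two wording changes:

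1. In 12.6, add *significant liver disease, current or past* to item 5 or item 6, with *significant* defined by the safety physicians.
2. In the rationale after 12.6, qualify the sentence that admits chronic stable illness with *other than significant liver disease*.

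The conflict could also be removed by cutting 14.1 back to match 12.6. Carrying the rule into 12.6 is preferable, because 14.1 gives a drug-specific safety reason for it and nothing in the documents withdraws that reason.

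The cost is one wording amendment and no new test. There may be a few more screen failures, and none if sites already apply 14.1. Even in the worse ineligibility case with five more failures, power before dropout stays just above 0.80.
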